11.1. Potential Risks

11.1.1. Health Risks

The following are known potential health risks associated with the NURO system and PTNM therapy:

- Discomfort and pain (including throbbing pain) at, or near, the stimulation site, including the patient's lower leg and foot
- Bleeding at the needle site
- Redness/inflammation at, or near, the stimulation site
- Numbness of toes
- Stomach ache

11.1.2. NURO System Warnings

To avoid risks to study subjects and system users, Investigators and site personnel should be aware of the following.

1. The provided Instructions for Use is NOT a comprehensive reference to therapeutic techniques for the indications noted for the NURO system. Section 11.1 will only be revised based on significant new safety information added to the Instructions for Use. Refer to the current Instructions for Use for complete contraindications, warnings and precautions.
2. Investigators and site personnel should be familiar with appropriate application and techniques involved in the use of the NURO system and needle in the delivery of Percutaneous Tibial Neuromodulation.
3. Do not use the NURO system or needle if the skin in the area of use is inflamed, infected, or otherwise compromised. Monitor subjects during therapy session for pain or skin irritation/inflammation. Discontinue use of the NURO system if the subject complains about these symptoms or any other discomfort.

Confidential

4. Do not use any part of the NURO system to apply stimulation across or through the head, directly on the eyes, covering the mouth, on the front of the neck (especially the carotid sinus), or on the chest, upper back or crossing over the heart. The application of the ground pad near the thorax may increase the risk of cardiac fibrillation.
5. Subjects should not spend more than 30 minutes in therapy mode during a single therapy session.
6. The subject should remain comfortably seated, or in a supine position, for the duration of the therapy session. The subject should not rise or walk until the therapy session is complete, because mobility during therapy session has not been assessed.
7. Do not use the NURO system if any component or accessory is loose or damaged, including the rear electrode snap or internal battery.
8. Do not use the NURO system if its packaging has been opened or altered. If packaging has been opened or altered, contact Medtronic.
9. Do not reuse the single-use needle, needle holder, or ground pad.
10. Dispose of used needle, needle holder, and ground pad accessories in bio-hazardous material disposal container.
11. Simultaneous connection of a patient to high frequency surgical equipment may result in burns at the site of the ground pad and/or needle and possible damage to the NURO device.
12. Device operation in close proximity (e.g. 1 meter) to short wave or microwave therapy equipment may produce instability in the NURO device output.
13. The NURO device has electric shock protection, type "Internally Powered Equipment" per IEC 60601-1.
14. The NURO device enclosure is type IPX0 and does not protect against the ingress of water. Do not use the NURO device in or around water.
15. For recharging, only use the wall charger provided with the NURO device. Use of a different charger could result in electrical shock or damage to the device.
16. Do not operate the NURO device with anything plugged into the USB port. Do not insert the needle into the micro USB port.
17. The following are known potential health risks associated with this type of device and therapy: discomfort and pain near needle site, bleeding near needle site, redness/inflammation near needle site, numbness in toes, and stomach ache.
18. The NURO device has no serviceable parts. No modification is allowed. Opening the case could lead to electrical shock, device damage, or other risks.
19. Do not exceed the recommended therapy session time of 30 minutes per session.
20. Do not excessively bend or kink the device cable. Always inspect device cable for signs of wear or damage before use. If wear or damage is found, discontinue use and return the NURO device to Medtronic.
21. No modification of this equipment is allowed.
22. Use only the ground pad listed in the IFU. This pad is sized to not to exceed 2 mA/cm² for the NURO device.

Confidential

11.1.3. NURO System Contraindications

In order for therapy to be effective and to avoid any possible problems or complications, the NURO system is contraindicated for use on patients who have the following history or conditions (see study exclusion criteria):

1. Subjects prone to excessive bleeding
2. Subjects with pacemakers or implantable defibrillators
3. Subjects with nerve damage that could impact either percutaneous tibial nerve or pelvic floor function
4. Subjects who are pregnant or planning to become pregnant while using this product
5. The NURO system is not intended for intra-cardiac or trans-thoracic use.
6. Concurrent use of medical monitoring equipment during stimulation is not recommended.
7. The NURO system is not suitable for use in the presence of a flammable anesthetic mixture with air or with oxygen or nitrous oxide.

11.1.4. NURO System Precautions

- Prior to using the NURO system, read and understand all instructions.
- Caution should be used for patients with suspected or diagnosed heart problems, especially those relating to the pacing or electrical functioning of the heart.
- Medical electrical equipment needs special precautions regarding electromagnetic compatibility (EMC) and needs to be installed and placed into service according to EMC guidelines provided.
 - a. Portable and mobile radio frequency (RF) communications equipment can affect medical electrical equipment.
 - b. Investigators and site personnel should assure the NURO system is used in an appropriate environment.
 - i. Portable and mobile RF Communications equipment (i.e. cell phones) should not be used at close distances.
 - ii. Power frequency magnetic fields should be at levels characteristic of a typical commercial, hospital or clinic environment.
- Always start and restart stimulation at the lowest settings and adjust as necessary. Do not return to any previous setting without observing the patient's responses.

Reporting of adverse events and device deficiencies should follow the requirements outlined in the adverse event assessment section of the study protocol.

There may be risks or side effects which are unknown at this time.

If a subject becomes pregnant while using the NURO system, there may be risks to her or her unborn baby. These risks are currently unknown. If the Investigators becomes aware that a subject is pregnant during the course of the study, the subject should be exited from the study.

Confidential

11.2. Potential Benefits

Subjects may not receive any direct medical benefit from participation in this study but subjects will receive additional medical oversight of treatment. Participation in this study will not provide greater benefit than if the subject was receiving PTNM therapy with the NURO system outside of the study. Information from this study might help researchers further understand PTNM therapy. The benefit to subjects participating in this study, and to future patients, resides in the knowledge gained from this study related to the safety and efficacy of this therapy when used in OAB drug naïve patients.

11.3. Risk-Benefit Rationale

Participation in this study will not expose the subject to greater risks than if he/she were receiving PTNM therapy with the NURO system outside of the study. There might be other discomforts and risks related to PTNM and/or this study that are not foreseen at this time.

Subjects may find that some of the questionnaires or completing the urinary voiding and fecal diaries are embarrassing.

12. Adverse Event Assessments

12.1. Definitions/Classifications

Any adverse event meeting the definition of: serious, device related, and/or procedure related as well as all device deficiencies will be considered reportable for this study. Adverse events and device deficiencies are defined as follows:

Term	General
Adverse Event (AE)	Any untoward medical occurrence, unintended disease or injury, or untoward clinical signs (including abnormal laboratory findings) in subjects, users or other persons, whether or not related to the medical device under investigation.
Adverse Device Effect (ADE)*	Adverse event related to the use of the medical device under investigation.
Device Deficiency (DD)*	Inadequacy of a medical device with respect to its identity, quality, durability, reliability, safety or performance. Device deficiencies include malfunctions, misuse or use errors, and inadequate labeling. 
▪ Malfunctions: Failure of the medical device under investigation to perform in accordance with its intended purpose when used in accordance with the instructions for use or Clinical Investigational Plan (CIP)▪ Use Error: Act or omission of an act that results in a different medical device response than intended by the manufacturer or expected by the user

Confidential

SERIOUSNESS	
Serious Adverse Event (SAE)*	
An adverse event that
 
 a) led to a death, b) led to a serious deterioration in the health of the subject, that either resulted in: 
 1. a life-threatening illness or injury, or 2. a permanent impairment of a body structure or a body function, or 3. in-patient or prolonged hospitalization, or 4. medical or surgical intervention to prevent life threatening illness or injury or permanent impairment to a body structure or a body function. c) led to fetal distress, foetal death or a congenital abnormality or birth defect. 
Note: A planned hospitalization for pre-existing condition, or a procedure required by the CIP, without a serious deterioration in health, is not considered to be a serious adverse event.

Serious Adverse Device Effect (SADE)*	Adverse device effect that resulted in any of the consequences characteristic of a serious adverse event
Unexpected Serious Adverse Device Effect (USADE)*	Serious adverse device effect which by its nature, incidence, severity or outcome has not been identified.
RELATEDNESS	
Relationship of Adverse Events	
The relationship of the adverse event to the study treatment (device, therapy) will be described using the following terms:
 
 • Not related • Unlikely • Possible • Probable • Causal relationship

*Reportable event categories that will be collected during this study

Confidential

12.2. Reporting of Adverse Events

Any adverse event meeting the definition of serious, device related, and/or procedure related as well as all device deficiencies as defined in above will be considered reportable for this study. The procedure is defined as each PTNM therapy session.

Worsening of OAB symptoms will be collected as part of the efficacy measures and are not considered a reportable adverse event.

All reportable adverse events will be classified using the following responsibility matrix:

Event Classification Responsibilities

What is Classified	Who Classifies	Classification Parameters
Relatedness	Investigator	Procedure related Device related Other
USADE potential	Medtronic	USADE
Seriousness	Investigator	SAE/SADE
Diagnosis	Investigator	Based on presenting signs and symptoms and other supporting data
	Medtronic	MedDRA term assigned based on the data provided by investigator

All reportable adverse events must be recorded in the subject's medical record and on the Adverse Event and/or Device Deficiency eCRF and promptly reported to Medtronic. IRB reporting must be completed in accordance with the policies of the governing IRB.

Reports of adverse events and device deficiencies will include the following information, at a minimum:

- Date of event
- Diagnosis or description of the event
- Assessment of the seriousness and relationship to the product(s) under study
- Treatment
- Outcome and date or resolution

It is the responsibility of the Investigator to identify the occurrence of reportable adverse events and device deficiencies and to ensure the required information is accurately documented on the eCRF.

The clinical course of each adverse event must be followed until resolution or subject discontinuation from the study, whichever comes first. "Ongoing" adverse events and device deficiencies must be assessed at each protocol required visit, and new or updated information must be documented on the Adverse Event and Device Deficiency eCRF and promptly reported to Medtronic and if applicable to the IRB.

If necessary, the Investigator may report to the sponsor initially by telephone or email and follow-up with completed eCRFs and, if possible, copies of source documentation regarding the event (e.g., physician/nurse notes or summaries).

Medtronic study personnel will promptly review all reported adverse events and device deficiencies and if necessary request clarification and/or additional information from the Investigator. If Medtronic

Confidential

disagrees with the Investigator's assessment of the adverse event relationship to device and/or procedure, Medtronic study personnel will document the disagreement and report or ensure reporting of both opinions to IRB as necessary. All reported adverse events and device deficiencies will be reviewed by a Medtronic Medical Monitor to ensure consistent reporting.

13. Data Review Committees

This study will not use a Clinical Events Committee or Data Monitoring Committee. Instead, all reported adverse events and device deficiencies will be reviewed by a Medtronic Medical Monitor to ensure consistent reporting.

14. Statistical Design and Methods

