7.9. Evaluation of Objectives

7.9.1. Primary objective

This study will assess the efficacy of PTNM on UUI episodes collected using a voiding diary. The primary objective is to demonstrate a statistically significant reduction between baseline and following the 12th PTNM therapy session in the number of UUI episodes per day.

Hypothesis

$H_0: \mu_{12\text{th PTNM therapy session}} = \mu_{\text{baseline}}$

$H_a: \mu_{12\text{th PTNM therapy session}} \neq \mu_{\text{baseline}}$

Where μ_{baseline} and $\mu_{12\text{th PTNM therapy session}}$ are average UUI episodes per day at baseline and following the 12th PTNM therapy session respectively.

Endpoint definition

The average UUI episodes per day collected at baseline and following the 12th and final PTNM therapy session will be used as the endpoint for the primary objective. Average UUI episodes per day will be calculated by summing all reported leaks and dividing by the total number of days of diaries.

For a diary to be included in the analysis, it needs to have complete leak and/or void episode entries for at least one day. For any reported episode if leak or void is not indicated, the diary of that day will not be included.

Data collection and analysis methods

Diary data collected at baseline and after the 12th PTNM therapy session will be used for the primary endpoint analysis. Reduction in average UUI episodes per day from baseline will be calculated for each subject after the 12th PTNM. The paired t-test or the Wilcoxon signed-rank test will be used to evaluate the changes after testing for data normality by calculating Shapiro-Wilk W statistic. A statistical test is deemed significant if the P value is less than 0.05. Primary analysis method will be completers (with no imputation of missing data). Sensitivity analyses will be conducted with the adjusted worst-case method and per protocol analysis.

Determination of subjects for analysis

Qualified subjects with diary data from both baseline and the 12th PTNM therapy session will be included in the primary analysis for this objective.

In addition to the primary analysis, two sensitivity analyses will be performed:

- Adjusted worst-case analysis, in which,
 - a. For subjects who received the study therapy and withdrew early due to device or therapy/procedure -related adverse events, or treatment unsuccessful, the 12th PTNM therapy session data point will be set to subject's baseline assessment.

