 - b. For subjects who received the study therapy and exit the study early due to all other reasons (i.e. adverse events not related to the device or therapy), and for subjects who missed the 12th PTNM therapy session or fail to provide the relevant data for 12th PTNM therapy session, the Last Observation Carried Forward (LOCF) method will be used to impute the missing data.
 - c. Subjects who exit the study prior to the initial NURO PTNM therapy session will be excluded from this sensitivity analysis
- Per protocol sensitivity analysis which will be based on the completers dataset, but will exclude those subjects who take OAB medications in the study. Use of OAB medications will be captured as a protocol deviation.

Besides PTNM session 12, diary data are also collected for PTNM Session #1, #4, and #8. Reduction in number of UUI episodes from baseline will be summarized for each follow up visit (PTNM session #1, #4, #8 and #12) when the diary data is collected with no imputation of missing data (completers analysis).

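### Protocol 12.2 exempts OAB worsening from AE reporting without condition, in conflict with 12.1, and rule (a) of the adjusted worst-case analysis resets worsened treatment failures to baseline

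*Protocol*

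**What the plan says.** **Safety reporting.** Protocol 12.1 sets the general rule: "Any adverse event meeting the definition of: serious, device related, and/or procedure related as well as all device deficiencies will be considered reportable". Protocol 12.2 repeats it and, in its next paragraph, makes an exception: "Worsening of OAB symptoms will be collected as part of the efficacy measures and are not considered a reportable adverse event". The exception is not limited to worsening that is non-serious or unrelated. Section 5.2 evaluates safety through reportable events. Section 13 provides for no events committee or data monitoring committee, only a sponsor medical monitor who reviews the events that are reported.

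**Efficacy analyses.** The primary analysis (SAP 7.9.1) uses subjects with both a baseline and a post-session-12 diary, without imputation. UUI and voids are tested and summarized as reductions. OABq is tested as change and summarized by session as improvement. PGI-I (SAP 7.9.3.4) is tabulated in all seven categories and also with the three worse categories pooled, once, after session 12, in subjects with data.

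**Adjusted worst-case analysis.** Rule (a) applies to treated subjects who "withdrew early due to device or therapy/procedure -related adverse events, or treatment unsuccessful". It scores each of them as having no change, because "the 12th PTNM therapy session data point will be set to subject's baseline assessment". Under rule (b), other early exits and missing session-12 data are filled by LOCF. SAP 7.9.2 applies the same sensitivity analyses to voids and OABq.

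**The concern.** An investigator who sees worsening that is serious, or that looks related to the device or the session, has two opposite instructions. If the exemption is followed, the event does not reach the medical monitor, who is the only designated safety reviewer. The protocol's reason for accepting this is that the efficacy measures will capture worsening, so it matters whether they do.

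The adjusted worst-case analysis is also meant to test the completers result against informative drop-out. Under rule (a), the subjects whose drop-out is most informative can be scored better than their own data show. The study is meant to contribute "the knowledge gained from this study related to the safety and efficacy of this therapy when used in OAB drug naïve patients", and both matters bear on that aim.

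**Working it through.** No stated figure decides this point. The inputs borrowed below are the planned reduction of 0.75 UUI episodes/day, SD 2.2, attrition of about 20% and up to 120 subjects (Protocol 14.1.1, SAP 6). They are consistent with the plan's sample size: the normal approximation gives (2.2 × (1.960 + 1.282) / 0.75)² = 90.4, so 91, and the exact t calculation gives 93 with power 0.902, as stated.

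**Step 1. The two reporting rules side by side**
- Related or serious event of any other kind: reportable (12.1, 12.2).
- Worsening of OAB symptoms, whether related, serious or neither: not reportable (12.2).
- Overlap: worsening that is serious or judged related falls under both. The text gives no order of precedence.

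**Step 2. Where worsening would show in the efficacy outputs**
- UUI, voids, OABq: summaries of reduction, change or improvement; no count of worsened subjects is specified.
- UPS, PPBC: category counts by visit; no within-subject shift.
- SAGA follow-up: end of study only, and rated against expectation, not against baseline.
- PGI-I: a direct count of subjects rating themselves worse, but end of study only.
- Early withdrawals: their diaries from sessions 1, 4 and 8 enter the by-visit summaries, and exit reasons are reported (SAP 7.1.1). The worsened subjects among them are not counted.

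**Step 3. Rules (a) and (b) on identical data**

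Take two subjects with baseline B and last diary L = B + d, with d > 0 (worse).
- Exit for a related adverse event or unsuccessful treatment, rule (a): imputed value B, change 0.
- Exit for an unrelated reason, rule (b): imputed value B + d, worse by d.

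With the same observed data, the treatment failure is scored better by d. If L is below B (improved), the order reverses: rule (a) gives change 0 and LOCF would give an improvement. Rule (a) is therefore too favourable only when the last diary is worse than baseline.

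**Step 4. Effect on the sensitivity estimate**

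If w of N treated subjects fall under rule (a) with a last diary worse by d on average, replacing B with the worse of B and L lowers the mean reduction by w × d / N. The documents give neither w nor d, so the following is an assumed range.
- N = 120; completers 0.80 × 120 = 96, with mean reduction 0.75; all 24 others fall under rule (a).
- Rule (a) as written: (96 × 0.75 + 24 × 0) / 120 = 0.60.
- With the worse of B and L: 0.60 − w × d / 120.

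| w | d = 1 | d = 2 | d = 3 |
|---|---|---|---|
| 6 | 0.55 | 0.50 | 0.45 |
| 12 | 0.50 | 0.40 | 0.30 |
| 24 | 0.40 | 0.20 | 0.00 |

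The difference runs from 0.05 to 0.60 episodes/day. The upper end requires every drop-out to be a rule (a) exit who is 3 episodes/day worse; it is a bound on the assumed range, not an expectation.

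**The case against.** The strongest case against the point is that 12.2 can be read as a deliberate, specific exception for the study's own endpoint symptoms, in an on-label, single-arm, post-market study. The SAE definition is demanding, and OAB worsening would rarely meet it. SAP 7.10 also summarizes SAEs for all enrolled subjects, related or not. This lowers the likely number of affected events. It does not settle which rule governs serious or related worsening, and the SAE summary depends on the same collection of reportable events.

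Four stronger conclusions are tempting, and the documents do not support them.
- **That no planned output counts worsened subjects.** PGI-I does, with an explicit pooled worse group.
- **That a subject who worsens and leaves disappears from every table.** Diaries and questionnaires obtained before exit enter the by-visit summaries, and exit reasons are reported. The SAP does not name the summary statistics, so a range, if shown, could reveal increases.
- **That rule (a) inflates the primary result.** It acts only in a sensitivity analysis, and only for two groups of exits. The primary analysis leaves out subjects without a session-12 diary for a different reason: it is restricted to completers.
- **That a given share of subjects will be harmed.** With normal changes, mean reduction 0.75 and SD 2.2, Φ(−0.75/2.2) = 0.367, or about 34 of 93 with more UUI episodes than at baseline. That share rests on an assumed continuous normal curve for a short diary count and includes diary noise and natural variation. Without a control arm it does not measure harm.

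A separate table of worsened subjects is therefore desirable rather than necessary.

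**Conclusion.** The point holds on two counts. First, the unconditional exemption in Protocol 12.2 contradicts the reporting rule in 12.1 and 12.2 for worsening that is serious or judged device- or procedure-related. The efficacy measures offered in its place cover worsening only in part. Second, rule (a) is not worst-case for subjects whose last diary is worse than baseline, and it scores those treatment failures more favourably than unrelated exits with the same diary.

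The size of the second effect is w × d / N, which cannot be derived from the documents; the 0.05 to 0.60 episodes/day above rests on assumed w and d. If no rule (a) exit has a last diary worse than baseline, the effect is zero. Nothing here shows that adverse events are being suppressed, that the device causes worsening, or that the sample size or the primary test is wrong.

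**What to change.** 1. **Rule (a), SAP 7.9.1.** Set the session-12 value to the worse of the baseline value and the last observed value. Apply this to UUI and to the voids and OABq endpoints that reuse the rule, taking worse in the direction of each scale's scoring. Subjects whose last value is better than baseline, or who have no post-baseline value, stay at baseline as now. Protocol 14.3 carries the same imputed value, so amend it too or record the departure in SAP 7.11, which currently reports no changes.
2. **Protocol 12.1 and 12.2.** Reconcile the two sections, stating explicitly how worsening that is serious or judged device- or procedure-related is to be handled.
3. **Optional.** Report descriptively the number and percent of treated subjects whose last available diary is worse than baseline, including early exits. Add a note that, without a control arm, this cannot separate harm from natural variation.

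The cost is one changed imputation phrase, one protocol sentence and, if wanted, one table from diaries already collected. Visits and sample size are unchanged. The downside is a possibly slightly less favourable sensitivity estimate and, depending on how 12.2 is reconciled, a few more adverse event forms.
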